8.4. Data Sources

This is a retrospective study of existing healthcare data collected; no participants will be actively enrolled and there will be no collection of any primary data. All pseudonymized data will be entered/collected in a standardized case report form (CRF) designed specifically for this study. Data will be collected from individual patient medical records maintained in the Centre according to clinical practice in paper or electronic version. An electronic case report form (eCRF) will be utilized to ensure efficient data collection and management. Data collection will be performed by trained person who are familiar with the study protocol and the clinical data being collected. These individuals will be responsible for accurately entering the pseudonymized data into the eCRF.

The data collection process will involve reviewing patient medical records and extracting relevant information according to predefined criteria outlined in the study protocol. The pseudonymized data will be collected from site and will be processed for further analysis. For pseudonymization, each participant will have a specific code. Only the site investigators will be able to link the code with the participant.

Hospitalizations and emergency department visits due to CHF will be ascertained by the primary investigator using ICD codes and supporting hospital records. The primary investigator will verify that the event was primarily caused by chronic heart failure, based on the patients' history, laboratory results, and medications recorded in the discharge hospitalization or emergency summary form.

The validity of the recording and coding of the data will be ensured through several measures. First, the CRF will be designed to capture standardized clinical information, reducing variability in data entry. Second, the study site team responsible for data collection will undergo training to ensure consistency and accuracy in data abstraction. Third, quality review by CRO will be conducted to verify the accuracy and completeness of the recorded data.

8.5. Study Size

[REDACTED]

Furthermore, to minimize selection bias, all patients diagnosed with ATTR-CM treated with tafamidis in this center and who meet the inclusion criteria will be eligible during the 24 months planned for enrollment procedures and until the target number of enrolled patients is reached according to the planned timeline.

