Data source: Pseudonymized data will be entered in CRF from individual patient medical records maintained in a single center in Turkey according to clinical practice. Data will be collected using electronic case report form (eCRF).

Sample size: Due to the absence of a priori hypothesis, sample size calculations are not applicable, and no formal sample size calculation has been performed. According to the descriptive nature of the study, we have planned a sample of around 70 subjects approximating 10% of the entire population diagnosed with ATTR-CM in Turkey, with no formal calculation related to a specific endpoint.

Data analysis: Descriptive statistics will be reported and no effort to determine statistical significance will be made.

Milestones:

Milestone	Planned Date
Registration in the HMA-EMA Catalogues of RWD studies	30 July 2025
Start of data collection	16 October 2025
End of data collection	30 June 2026
Final study report	31 December 2026

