4. AMENDMENTS AND UPDATES

Version Identifier	Date	Amendment Type (substantial or administrative)	Protocol Section(s) Changed	Summary of Amendment(s)	Reason				
2.0	16 Dec 2025	Substantial	5. Milestones	Start of data collection, end of data collection, and final study report dates are postponed per the actual data collection start date.	Completion of site agreement and therefore the SIV were completed later than initially planned. Due to these, data collection has started later than initially planned and actual data collection start date is mentioned in the revised version. Due to the increase in subject number, longer duration is now anticipated for completion of data entry. Therefore, dates of end of data collection and final study report are also postponed accordingly.				
						Substantial	3. Abstract	Sample size is increased to 70.	Since the start of data collection is postponed, number of eligible patients at the study site has increased during that duration. To obtain more comprehensive data, it is decided to include all eligible patients to the study.
						Substantial	8.5. Study Size		
						Substantial	3. Abstract		
						Substantial	8.2. Setting		
						Administrative	8.3. Variables		
Administrative	8.3. Variables	Assessment period of the variable “NYHA Class” is corrected to include the “follow-up	Due to an error and oversight, “follow-up assessment period” of the “NYHA Class” was initially omitted and now updated accordingly.						

Version Identifier	Date	Amendment Type (substantial or administrative)	Protocol Section(s) Changed	Summary of Amendment(s)	Reason
		Administrative	8.3. Variables	Operational definition of the variable "Carpal Tunnel Syndrome" is changed to "History of Carpal Tunnel Syndrome (yes/no/missing) as documented in the source data".	Due to an error and oversight, operational definition of the "Carpal Tunnel Syndrome" was initially mentioned incorrectly and now updated accordingly.
		Administrative	8.3. Variables	Variable name "Tafamidis treatment start date" is changed to "Tafamidis treatment prescription date".	Due to an error and oversight, variable name and operational definition of the "Tafamidis treatment prescription date" were initially mentioned incorrectly and now updated accordingly.

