Approximately seventy (70) subjects who meet the inclusion and exclusion criteria detailed below will be included in the study. The inclusion and exclusion criteria were established based on the diagnosis of ATTR-CM disease and the evaluation of tafamidis treatment outcomes as outlined in the study objectives. The study population formed in light of these criteria is expected to represent the source population and the population of Turkey.

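### Section 8.5 makes every qualifying patient eligible to limit selection bias, but the same sentence ends inclusion at a target number; this matters only if more than about 70 patients qualify.

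*Protocol*

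**What the plan says.** The visible part of Section 8.5 is a single sentence with three parts:

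- The aim and scope: "to minimize selection bias, all patients diagnosed with ATTR-CM treated with tafamidis in this center and who meet the inclusion criteria will be eligible".
- A period: "during the 24 months planned for enrollment procedures".
- A stop: "until the target number of enrolled patients is reached according to the planned timeline".

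The target appears in two other places. Section 8.2 states: "Approximately seventy (70) subjects who meet the inclusion and exclusion criteria detailed below will be included in the study". The abstract states: "we have planned a sample of around 70 subjects approximating 10% of the entire population diagnosed with ATTR-CM in Turkey", and adds that "sample size calculations are not applicable, and no formal sample size calculation has been performed".

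Several other sections bear on the point:

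- Section 8.2.1 limits diagnosis to 1 January 2023 to 1 January 2025.
- Section 8.4 says that the study uses existing records and that nobody is actively enrolled.
- Section 8.2 closes follow-up on 30 September 2025, and Section 5 starts data collection on 16 October 2025.
- Section 8.6, under data types, describes chart review as covering all eligible patients.
- Section 8.7 gives the analyses: events per patient-year for the hospitalisation and emergency outcomes, and Kaplan-Meier for survival.

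**The concern.** Taking everyone who qualifies protects against selection only if nothing cuts it short. A stop at a count removes that protection once the number who qualify exceeds the count. The wording suits prospective accrual, where patients arrive over time and recruitment has to close at some point. Here the diagnosis window is already closed, and the site can list everyone who qualifies before opening a chart.

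What is at stake is who makes up the cohort. Apart from events still running at the cut-off, every outcome within follow-up has happened before abstraction begins. The investigator enters the data (Section 8.6) and also judges whether events are due to heart failure (Section 8.4). If some qualifying charts are left out, and the visible text gives no order for taking them, membership depends on which files are opened first. That could affect the primary rate, the survival curve, and the expectation in Section 8.2 that the cohort represents its source population.

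**Working it through.** **Can the planned size be reproduced?** No. The protocol gives no precision target, effect size or power, so no formula leads to 70. The only arithmetic on offer is that 70 at 10% implies about 70 / 0.10 = 700 diagnosed patients nationally. That says nothing about how many qualify at this centre.

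**Does the stop fit the design?** Three comparisons:

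1. Section 8.5 speaks of 24 months of enrolment. Data collection in Section 5 runs from 16 October 2025 to 30 June 2026, which is 257 days, or 257 / 30.44 = 8.4 months. The diagnosis window in Section 8.2.1 is 731 days, or 731 / 30.44 = 24.0 months. The 24 months match only the diagnosis window.
2. Section 8.5 allows inclusion to end at a count. Section 8.6 describes review of every eligible patient's chart. The two agree only if the number who qualify does not exceed the target.
3. Follow-up closes 16 days before data collection starts, so any choice among charts is made after the outcomes.

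**How many could be left out?** The number who qualify, N, is not given; 70 to 100 is an assumed range. With a strict stop at 70, the share left out is (N − 70) / N.

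**Does the order of charts matter?** For illustration, assume that diagnosis dates are spread evenly over the window, tafamidis starts at diagnosis, and nobody dies, stops or is lost. Potential follow-up to 30 September 2025 then runs from 272 days (8.94 months) to 1,003 days (32.95 months), with a mean of (32.95 + 8.94) / 2 = 20.9 months for the full cohort. With f = 70 / N:

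- earliest-diagnosed 70: mean = 32.95 − 24.02 × f / 2
- latest-diagnosed 70: mean = 8.94 + 24.02 × f / 2

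For N = 80, f = 0.875 and 24.02 × 0.875 / 2 = 10.51, which gives 32.95 − 10.51 = 22.4 months or 8.94 + 10.51 = 19.4 months.

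| N assumed | Left out | Share | Mean follow-up, earliest 70 | Mean follow-up, latest 70 |
|---|---|---|---|---|
| 70 | 0 | 0% | 20.9 | 20.9 |
| 75 | 5 | 6.7% | 21.7 | 20.1 |
| 80 | 10 | 12.5% | 22.4 | 19.4 |
| 90 | 20 | 22.2% | 23.6 | 18.3 |
| 100 | 30 | 30.0% | 24.5 | 17.3 |

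Without the stop, the mean is 20.9 months for any N. A constant delay from diagnosis to prescription would shorten all these means alike and leave their differences unchanged.

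**Which way could bias go?** Take 80 qualifying patients, 16 of whom have died (both figures assumed). If all 64 living patients are abstracted first, 6 of 70 included patients are dead (8.6%). If the deceased are abstracted first, it is 16 of 70 (22.9%). The full cohort has 16 of 80 (20.0%). These are the two extremes of perfect sorting on a crude proportion. They show that the direction is open. They do not estimate the error in events per patient-year or in the Kaplan-Meier curve.

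**The case against.** The strongest reply is that the clause may never bind. The size is approximate in both places where it is given. The amendment table explains the rise to 70 by growth in the number of eligible patients and says "it is decided to include all eligible patients to the study", which suggests that 70 is close to the site's own count. The diagnosis window closed before version 2.0, so no new diagnoses can add to it, although a patient diagnosed in the window could still qualify by starting tafamidis later. All of this stands, and it makes the point conditional.

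Three further replies carry some weight:

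- The sentence says that patients are eligible, not that they are included, and it can be read as describing expected accrual. However, its stated purpose is met only if everyone eligible is included.
- Part of Section 8.5 is blacked out and may explain the target. That text cannot be relied on either way, and the visible stop remains.
- Section 8.9 already concedes possible selection bias and incomplete representation of patients lost to follow-up or not completing treatment. It does not link this to the stop, which is avoidable.

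A reader might infer more than the protocol supports, in three ways. The first is that bias would be favourable because living, attending patients are abstracted first; nothing in the protocol says so. The second is that the cohort would be the first patients to come; no order is stated. The third is that Section 8.5 contradicts the amendment table; that table describes changes and their reasons, so it serves only as context.

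**Conclusion.** The point holds in a limited form. Section 8.5 states a guard against selection bias and a stop rule that defeats it whenever more than about 70 patients qualify. The chart-review statement in Section 8.6 fits the guard and not the stop. If about 70 qualify, the effect is nil. Under assumed totals of 75 to 100, a strict stop at 70 would leave out 6.7% to 30.0% of the cohort. It could bias the event rate and survival in either direction, by an amount that the protocol does not allow anyone to calculate. The conclusion rests on reading the stop as written and on the assumed totals. It does not rest on the redacted text or on the amendment table.

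**What to change.** In Section 8.5:

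1. Delete the clause that ends inclusion at the target number.
2. State that all patients at the centre diagnosed from 1 January 2023 to 1 January 2025 who meet the criteria will be included, and that about 70 is the expected number and not a limit.
3. Replace "during the 24 months planned for enrollment procedures" with a reference to that 24-month diagnosis window.

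In practice, the site would list everyone in the window with a tafamidis prescription and work through the whole list.

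The cost is one sentence, plus a few more charts if more than 70 patients qualify. There is no patient contact, and because no formal calculation underlies 70, exceeding it disturbs no statistical design. If about 70 qualify, the change costs nothing beyond the wording.

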8.6. Data Management

Data management will be performed by the CRO acting on behalf of Pfizer.

Data Collection and Entry: Patient data will be collected retrospectively from electronic health record systems maintained at the single participating center. The treatment protocol notes data will be collected in the eCRF. The data collection period is between January 2023 and September 2025. Patient data will be collected during the baseline diagnosis period and then throughout the treatment period (while the patient is under tafamidis treatment) during follow-ups period. The study does not involve any patient contact and will not impact the care patients receive. Preidentified data regarding the patients will be collected in electronic Case Report Forms eCRF and analyzed to accomplish the proposed study objectives.

Data will be collected on the e-CRF application, which will be prepared based on the CRF that will be developed specifically for this study. The e-CRF will meet the scientific, regulatory, and logistical requirements of the study before it is used to record data for this study. Before using the e-CRF, all users will receive training on the system and study specific training.

The single investigator from a single center and a site coordinator will be defined in the system. Form controls will be used for the appropriate data fields (for data fields with clear boundaries and content), this will prevent any data entry outside the limits set for the investigator. For data fields that cannot be limited by form controls but have boundaries, automatic form controls will be provided in the system.

All data required for the study, including nurses' measurements, patient demographics and necessary previous medical records will be recorded to the e-CRF manually by the investigator. The investigator is responsible for the accuracy of these manually recorded data.

During patient data entry, the faulty/missing data scan will be performed by the e-CRF automatically. In this way, any form with faulty or missing data will not be allowed to send data to e-CRF, and warning messages will be displayed on the computer screen to the person entering the data to ensure that he/she enter data correctly and completely.

Data cleaning and, if necessary, source data verification will be conducted. After cleaning, the database will be locked, and the data will be extracted in the appropriate format.

Patient identity should not be discernible from the data provided on the e-CRF and documents that will be stored as source data on patient file of this study. All data collected will be approved and signed by the investigator at the investigational center. This approval acknowledges the investigator's review and acceptance of the data as being complete and accurate.

Data Types: Collected data will include sociodemographic characteristics, clinical parameters, diagnostic results, treatment details, and patient outcomes, as detailed in the study protocol. The medical charts of all eligible patients were reviewed for the following data: demographic characteristics, lab tests, serum free light chain levels, Serum/urine protein/immunofixation electrophoresis, genetic tests, ECG, Echocardiography, Scintigraphy results SPECT results.

Data Entry: Data will be entered into a secure, password-protected electronic database ensuring compliance with relevant regulations and guidelines.

Data Validation: All data entries will be double-checked for accuracy by designated personnel. Any discrepancies will be discussed with investigator resolved by cross-referencing the source documents.

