Rhythm	Patient Baseline ECG Parameters, Secondary Objective	Baseline Assessment Period	Nominal	Electronic health records or physical patient file	Heart rhythm 1-Normal Sinus Rhythm 2-Atrial Fibrillation
Pseudo infarct Sign	Cardiac Red Flag, Secondary Objective	Baseline Assessment Period	Nominal	Electronic health records or physical patient file	a Q-wave inversion on an electrocardiogram that mimics an

						acute myocardial infarction (present: Yes; or not: No)
Voltage Mismatch	Cardiac Red Flag, Secondary Objective	Baseline Assessment Period	Nominal	Electronic health records or physical patient file	Incompatibility between low QRS voltage on ECG and increased LV wall thickness on echocardiography (present: Yes; or not: No)	
Conduction Disturbance	Cardiac Red Flag, Secondary Objective	Baseline Assessment Period	Nominal	Electronic health records or physical patient file	The cardiac area refers to any abnormality in the electrical conduction system of the heart (present: Yes; or not: No)	
EF = Ejection Fraction	Patient Baseline Echo Parameters, Functional Outcome, Secondary Objective	Baseline, Index, Follow up Assessment Period	Continuous	Electronic health records or physical patient file	The percentage of blood that is ejected from the left ventricle of the heart with each contraction, as recorded in the source echocardiography data %	
IVS (Interventricular ar Septum)	Patient Baseline Echo Parameters, Functional Outcome, Secondary Objective	Baseline, Index, Follow up Assessment Period	Continuous	Electronic health records or physical patient file	The structure that separates the right and left ventricles of the heart, as recorded in the source echocardiography data mm	
LVEDD (Left ventricle end diastolic diameter)	Patient Baseline Echo Parameters, Secondary Objective	Baseline Assessment Period	Continuous	Electronic health records or physical patient file	The measurement of the diameter of the left ventricle at the end of diastole, as	

						recorded in the source echocardiography data mm
LVESD (Left ventricle end systolic diameter)	Patient Baseline Echo Parameters, Secondary Objective	Baseline Assessment Period	Continuous	Electronic health records or physical patient file	The measurement of the diameter of the left ventricle at the end of systole, as recorded in the source echocardiography data mm	

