Pericardial Effusion	Cardiac Red Flags, Secondary Objective	Baseline Assessment Period	Nominal	Electronic health records or physical patient file	Accumulation of fluid in the pericardial sac exceeding the physiological amount (present: Yes; or not: No)
Biatrial Dilatation	Patient Baseline Echo Parameters, Secondary Objective	Baseline Assessment Period	Nominal	Electronic health records or physical patient file	Enlargement of both atria, (present: Yes; or not: No)
Valve Thickening	Cardiac Red Flags, Secondary objective	Baseline Assessment Period	Nominal	Electronic health records or physical patient file	Increased thickness of heart valves, assessed via echocardiography (present: Yes; or not: No)
Tc99m PYP uptake; Perugini score	Patient Baseline Clinical Parameters,	Baseline Assessment Period	Ordinal	Electronic health records or physical patient file	Semi-quantitative visual scoring system for Tc99m PYP uptake, used

(PYP cardiac Scintigraphy Grade)	Secondary objective				to differentiate cardiac ATTR from AL amyloidosis (Grade 0-1-2-3)
Identification of hereditary vs. wild-type ATTR-CM (Wild - Variant)	Patient Baseline Clinical Parameters, Secondary objective	Baseline Assessment Period	Nominal	Electronic health records or physical patient file	Wild and Variant type of ATTR CM, this variable is defined by the TTR mutation test result, as recorded in the source data
TTR mutation variant (V30M, V122I, T60A, Ala81Thr, Arg34Gly, Other)	Patient Baseline Clinical Parameters, Secondary objective	Baseline Assessment Period	Nominal	Electronic health records or physical patient file	Mutation Type: V30M, V122I, T60A, Ala81Thr, Arg34Gly and other
6 min walking test m	Functional outcome, Secondary objective	Index, Follow up Assessment Period	Continuous	Electronic health records or physical patient file	Tests results as recorded in the source data
KCCQ Score per treatment (Kansas City Cardiomyopathy Questionnaire)	Functional outcome, Secondary objective	Index, Follow up Assessment Period	Ordinal	Electronic health records or physical patient file	Assessing physical limitations, symptoms, self-efficacy, social interference, and quality of life in heart failure patients.

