8.7. Data Analysis

The anonymously collected data of each patient cohort will be analyzed with an exploratory data analysis approach. The de-identified dataset will be analyzed using statistical software. Descriptive

statistics, survival analyses, and exploratory methods will be employed to address study objectives. Outliers and data inconsistencies will be reviewed and addressed before final analysis. Only descriptive statistics will be reported and no effort to determine statistical significance will be made.

Hospitalization and emergency department admission rates attributable to chronic heart failure, as well as hospitalization rates for cardiovascular-related illness, will be expressed as events per patient-year to account for variable follow-up durations.

Overall survival will be described using the Kaplan–Meier method, appropriately accounting for differing follow-up times and censoring; competing risks will not be considered.

Cardiac and extra-cardiac “red flags,” together with clinical and functional outcomes, will be described using means (standard deviations) for continuous variables and proportions for categorical variables.

Missing data will not be imputed; all analyses will be based on available data, with the number of missing observations reported for each variable where applicable.

Detailed methodology for summary and statistical analyses of data collected in this study will be documented in a statistical analysis plan (SAP), which will be dated, filed, and maintained by the sponsor. The SAP may modify the plans outlined in the protocol; any major modifications of primary endpoint definitions or their analyses would be reflected in a protocol amendment.

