8.8. Quality Control

Before the study launch, study personnel will review data collection and processing procedures, with all study-related trainings recorded in a training log.

The principal investigator and a designated CRO team will monitor the study data for accuracy and completeness, conducting periodic reviews to ensure adherence to the study protocol, quality of data collection, and completeness of datasets, following SOPs for all aspects of data collection, entry and data analysis consistency and reliability. The analytic dataset consisting of the collected data will be validated by the principal Investigator or designee who will verify the following:

- Review of illogical data or atypical values (incl. the values out of range and with different units/ information of what is indicated in Table 1. Variables of interests);
- Verification of conflicting data;
- Review of very high percentages of response as “not known” or “data not available”;
- Verification of accuracy of the collected data by comparison with the source documents.

CRO is responsible for following their own SOPs as well as Pfizer’s SOPs to ensure data quality and integrity, including archiving of statistical programs, appropriate documentation of data cleaning and validation of derived variables. Guidelines for data collection and data quality checks will be described in the Monitoring and Data Quality Oversight Plan.

A record of data quality problems and resolutions will be kept through documented meeting minutes.

All inconsistencies and/or data quality issues will be documented. Revisions of study documents will be noted in order to capture the change made, the change date, identification of the individual making

the change, as well as noting any further actions to be taken to identify and/or resolve additional data quality problems of this type.

Electronic Data will be stored in a secure, password-protected database with restricted access in compliance with all local applicable laws and regulations, with regular backups to prevent loss, physical paper version records will be stored in a locked, secure location accessible only to authorized personnel. Statistical programming and datasets used to generate study results will be archived with version control, ensuring reproducibility of analyses.

Data collection and processing will be limited to necessary data for study objectives, with data pseudonymized to protect participant privacy.

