8.9. Strengths and Limitations of the Research Methods

This study will provide insights into the clinical outcomes of ATTR-CM patients treated with tafamidis in Turkey. This localized focus on a unique population adds to the limited data on regional variations in the disease and treatment outcomes.

This study will have several limitations. Being a single-center study, the findings may not be generalizable to other centers, regions, or healthcare systems with different patient populations and practices. Medical records may have missing or incomplete information (e.g., certain biomarkers, imaging results, or medication adherence data).

Ascertainment of CHF hospitalization will be done by a principle investigator using all available records; potential misclassification of the reasons for hospitalizations is possible. To partially address the issue of misclassification, all CV hospitalizations will be captured and recorded in CRF as well. Emergency admissions for causes other than CHF will not be captured and analyzed. There is a potential, that some of the emergency admissions could be related to cardio-vascular causes, but full verification may not be possible; this will remain a limitation of the current study.

Only patients diagnosed and treated at the single participating center will be included, which could lead to a selection bias. Patients lost to follow-up or those who did not complete tafamidis treatment may not be fully represented.

The design of the study does not include a comparative arm and does not allow for robust causal conclusions related to tafamidis treatment effectiveness or safety.

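### The eCRF completeness stop and the Yes/No-only coding of most cardiac red flags leave no entry for 'not documented', so red-flag prevalence may be understated and missing counts for these fields uninformative

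*Protocol*

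**What the plan says.** **Data entry (section 8.6).** The eCRF scans each form and "any form with faulty or missing data will not be allowed to send data to e-CRF"; on-screen warnings then prompt the person entering data to correct and complete it. For fields with clear boundaries, form controls are set and "this will prevent any data entry outside the limits set for the investigator".

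**Analysis (section 8.7).** "Missing data will not be imputed; all analyses will be based on available data, with the number of missing observations reported for each variable".

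**Limitations (section 8.9).** "Medical records may have missing or incomplete information", with biomarkers and imaging results among the examples.

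**Quality control (section 8.8).** The list includes "Review of illogical data or atypical values (incl. the values out of range", judged against Table 1. It also includes a check for very high percentages of 'not known' or 'data not available' responses.

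**Coding (section 8.3, Table 1).** History-of-diagnosis comorbidities, carpal tunnel syndrome, peripheral neuropathy and lumbar stenosis are coded yes/no/missing. Pericardial effusion is defined as "Accumulation of fluid in the pericardial sac exceeding the physiological amount (present: Yes; or not: No"; pseudo-infarct sign, voltage mismatch, conduction disturbance and valve thickening use the same two answers. Rhythm is "Heart rhythm 1-Normal Sinus Rhythm 2-Atrial Fibrillation", although pacemaker history is a separate variable.

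**The concern.** This is a chart review, and the protocol itself expects holes in the charts. A rule that stops incomplete forms fits that setting only if every field accepts an explicit 'not documented' answer. Table 1 writes such an answer for the history items but not for most of the ECG and echo red flags.

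Describing red flags at baseline is a named secondary objective, reported as proportions. If a finding that was never looked for or never recorded is stored as absent, the proportion falls. The missing count meant to warn the reader shows nothing for that variable. No later analysis can separate the two once they share a code, so the SAP cannot repair it. For rhythm, a paced patient has no correct category.

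A smaller inconsistency of the same kind concerns limits: section 8.6 prevents entries outside set limits, while section 8.8 plans to review out-of-range values.

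**Working it through.** The protocol gives no figure on this point, so there is nothing to reproduce. The check is a count of codes, a side-by-side reading, and an illustration.

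**1. Count of Yes/No-only cardiac red flags** (NT-proBNP and troponin counted separately)

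- List in section 8.3.1: pseudo-infarct sign, voltage mismatch, conduction disorder and pericardial effusion are Yes/No; NT-proBNP, troponin and septal thickness are continuous. 4 of 7 = 57%.
- Role column of Table 1: valve thickening is added and septal thickness is not labelled a red flag. 5 of 7 = 71%.
- Union of the two lists: 5 of 8 = 63%.

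Most are Yes/No-only on each count. The continuous items are not affected by this coding. Outside the red flags, the 5-5-5 finding, biatrial dilatation and the three immunofixation items also have two answers only.

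**2. Do the sections fit together?**

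| Section | Treatment of a gap |
|---|---|
| 8.6 | form cannot be sent |
| 8.7 | gap is counted per variable |
| 8.8 | gap may appear as a non-response answer; fields not named |
| 8.9 | gaps are expected |
| Table 1, history items | missing code present |
| Table 1, items in step 1 | no missing code |

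These can all hold only if the items in step 1 also accept a non-response answer and section 8.6 treats it as complete. Neither is stated.

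**3. Illustration of the effect**

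Assumptions, none from the documents: true prevalence p; a share m undocumented, unrelated to presence of the finding; every undocumented case entered as No. The planned size of about 70 is from the protocol abstract. Then

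reported prevalence = p(1 − m), and the shortfall = p × m.

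| p | m = 5% | m = 10% | m = 20% | m = 30% |
|---|---|---|---|---|
| 30% | 28.5% | 27% | 24% | 21% |
| 50% | 47.5% | 45% | 40% | 35% |
| 70% | 66.5% | 63% | 56% | 49% |
| undocumented, of 70 | 3.5 | 7 | 14 | 21 |

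Take p = 50%, m = 20%. Undocumented: 70 × 0.20 = 14. Documented: 70 − 14 = 56, of whom 28 have the finding.

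- With a not-documented code: 28/56 = 50%, with 14 shown as not assessed. The reader can also form the bounds 28/70 = 40% and (28 + 14)/70 = 60%.
- With all 14 stored as No: 28/70 = 40%, with 0 shown as missing.

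**4. Limits.** Table 1 prints ranges, for example 100–100000 ng/L for NT-proBNP. Section 8.6 does not say that these are the limits its form controls enforce, and section 8.8 uses Table 1 for its out-of-range review. For any field where entry is blocked at the Table 1 range, that review would find nothing. Which fields those are is not stated.

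**The case against.** The strongest reply is that section 8.8 already foresees 'not known' and 'data not available' answers, so the stop in section 8.6 may block only blank fields. Table 1 holds operational definitions, and the CRF on which the eCRF is based is not shown. This stands in part: the eCRF may offer such answers on these items. But no section says so, and Table 1 writes the missing code where it wants one.

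Several stronger readings are tempting and are not supported:

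- *Abstractors must enter No.* No section orders this. Section 8.6.1 requires CRF data to match the chart, and source checks might catch an unsupported No.
- *All missing counts are meaningless.* Counts remain informative for items with a missing code and for any field that accepts a non-response answer.
- *Blocked forms lose whole patients.* Section 8.6 describes warnings that lead to correction; nothing says a record is dropped.
- *Table 1 ranges are hard limits.* This is not stated, as shown above.

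It is also fair that inclusion criterion 4 asks for complete records and that section 8.1 calls the data routine, which would make m small; section 8.9 still expects gaps. Finally, an ECG or echo report that is silent on a finding may mean it was absent. Excluding every silent report could then push prevalence upward. That stands, and calls for a coding rule.

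**Conclusion.** The point holds as an inconsistency between sections 8.6, 8.7, 8.8, 8.9 and Table 1. As written, for four listed cardiac red flags, valve thickening and some other items, not documented cannot be told from absent, and a paced rhythm has no code. Prevalence of these red flags may be understated, and their missing counts may say nothing.

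The size is unknown. The p × m shortfall (10 points at p = 50%, m = 20%) rests on assumed p and m, on documentation being unrelated to presence, and on every gap becoming No. The point touches a descriptive secondary objective. It should be settled while data entry is open, because the distinction cannot be recovered from the database afterwards.

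**What to change.** 1. In Table 1 and the eCRF, add 'not done/not documented' to every Yes/No-only item and 'other/paced' to rhythm. State how an available report that does not mention the finding is to be coded.
2. In section 8.6, say that these entries satisfy the completeness check.
3. In section 8.7, report each red flag as n/N assessed, with the number not assessed.
4. Reconcile sections 8.6 and 8.8: an out-of-range value raises a query and is accepted once confirmed against source.
5. Recheck against source the No answers, and the rhythm codes, already entered on these items.

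The cost is an eCRF configuration change, an edit to Table 1 and a sentence or two in each section named. Step 5 covers entries made since data collection began on 16 October 2025. Collection is planned to end on 30 June 2026; after database lock, the same correction would need a second chart review for up to about 70 patients.
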